## STUDY OUTLINE

Name of Sponsor/Company: Octapharma AG	
Name of Investigational Product: Octafibrin	Protocol Identification Code: FORMA-04
Name of Active Ingredient: Fibrinogen	Date of Final Protocol: 30-May-2017

Title of Study: Prospective, open-label, uncontrolled, Phase III study to assess the efficacy, safety, and pharmacokinetics of Octafibrin for on-demand treatment of acute bleeding and to prevent bleeding during and after surgery in paediatric subjects with congenital fibrinogen deficiency	
Indication: Congenital fibrinogen deficiency	
Number of Study Centres: Approximately 5 study centres worldwide.	
Study Duration: 3rd quarter 2015 to 3rd quarter 2020	Development Phase: III
Objectives:	
Primary:	

To demonstrate the efficacy of Octafibrin for on-demand treatment of acute bleeding episodes (spontaneous or after trauma)

	
Secondary:	

To determine the single-dose pharmacokinetics of Octafibrin in paediatric subjects with congenital fibrinogen deficiency

To investigate an association between the overall clinical assessment of haemostatic efficacy and the surrogate endpoint 'clot strength' or 'clot firmness' (referred to as 'maximum clot firmness' [MCF] in this protocol) via thromboelastometry (ROTEM). Therefore, MCF as surrogate efficacy parameter will be determined before and after the first infusion of IMP for treatment of a bleeding episode

To achieve a peak target plasma fibrinogen level of 100 mg/dL in minor bleeds and 150 mg/dL for major bleeds 1 hour post-infusion

To determine the response to Octafibrin based on incremental in vivo recovery (IVR)

To demonstrate the efficacy of Octafibrin in preventing bleeding during and after surgery

To assess the safety of Octafibrin in subjects with congenital fibrinogen deficiency, including immunogenicity, thromboembolic complications, and early signs of allergic or hypersensitivity reactions

	

Name of Sponsor/Company: Octapharma AG	
Name of Investigational Product: Octafibrin	Protocol Identification Code: FORMA-04
Name of Active Ingredient: Fibrinogen	Date of Final Protocol: 30-May-2017

Study Design: Multinational, multi-centre, prospective, open-label, uncontrolled, Phase III study.
Number of Subjects: At least 12 male or female paediatric subjects with congenital fibrinogen deficiency will be enrolled into the study and undergo PK assessment. Of these 12 subjects, at least 6 subjects will undergo on-demand treatment of 6 first bleeding episodes. Of these 6 subjects, at least 3 should be aged between 0 and <6 years and 3 should be aged between 6 and <12 years. In addition, at least 2 surgical procedures will be assessed.
Subject Selection Criteria: Inclusion criteria: 

1. Aged <12 years (at the start of treatment)

2. Documented diagnosis of congenital fibrinogen deficiency, expected to require on-demand treatment for bleeding or surgical prophylaxis:

– Fibrinogen deficiency manifested as afibrinogenaemia or severe hypofibrinogenaemia

– Historical plasma fibrinogen activity of <50 mg/dL or levels below the limit of detection of the local assay method.

3. Expected to have an acute bleeding episode (spontaneous or after trauma) or planning to undergo elective surgery

4. Informed consent signed by the subject's legal guardian

 Exclusion criteria: 

1. Life expectancy <6 months

2. Bleeding disorder other than congenital fibrinogen deficiency, including dysfibrinogenaemia

3. Prophylactic treatment with a fibrinogen concentrate

4. Treatment with:

– Any fibrinogen concentrate or other fibrinogen-containing blood product within 2 weeks prior to start of treatment for the PK phase, a bleeding episode, or surgery

– Any coagulation-active drug (i.e., non-steroidal anti-inflammatory drugs, warfarin, coumarin derivatives, platelet aggregation inhibitors) within 1 week prior to start of the PK phase or treatment for the bleeding episode or surgery, or as a planned or expected medication during the time period from Day 1 until 24 hours (i.e., 1 day) after the last Octafibrin infusion

Name of Sponsor/Company: Octapharma AG	
Name of Investigational Product: Octafibrin	Protocol Identification Code: FORMA-04
Name of Active Ingredient: Fibrinogen	Date of Final Protocol: 30-May-2017

5. Presence or history of:
  - Hypersensitivity to study medication
  - Deep vein thrombosis or pulmonary embolism within 1 year prior to start of treatment for the bleeding episode or surgery
  - Arterial thrombosis within 1 year prior to start of treatment for the bleeding episode or surgery
  - Hypersensitivity to human plasma proteins
  - Oesophageal varicose bleeding
  - End-stage liver disease (i.e., Child-Pugh score B or C)
6. Known positive HIV infection with a viral load >200 particles/µL or >400,000 copies/mL
7. Polytrauma 1 year prior to start of treatment for the bleeding episode or surgery
8. Diagnosis or suspicion of a neutralizing anti-fibrinogen inhibitor currently or at any time in the past
9. Acute or chronic medical condition which may, in the opinion of investigator, affect the conduct of the study, including subjects receiving immune-modulating drugs (other than anti-retroviral chemotherapy), such as alpha-interferon, prednisone (equivalent to >10 mg/day), or similar drugs, at study start
10. Treatment with IMP in another interventional clinical study currently or during the past 4 weeks

#### **Test Product, Dose, Mode of Administration, and Batch Number(s):**

In this study, *Octafibrin* will be administered as intravenous (i.v.) bolus injection. Continuous infusion is not allowed.

#### **PK Dose Schedule and Mode of Administration**

For PK assessments, subjects will receive a single intravenous infusion of 70 mg/kg body weight of *Octafibrin*.

#### **Octafibrin Treatment Dose Calculation**

*Octafibrin* will be individually dosed to achieve a recommended target fibrinogen plasma level dependent on the type of bleeding or surgery (minor or major). The dose will be calculated individually as follows:

$$\text{Fibrinogen dose} = \frac{[\text{Target peak plasma level (mg/dL)} - \text{measured level (mg/dL)}**]}{\text{Median response* (mg/dL per mg/kg body weight)}}$$

\* The median response in this dose calculation formula is the median incremental in vivo recovery reported for the PK of Octafibrin in the final analysis of study FORMA-01 which was calculated as 1.77.

\*\*The measured level for the first infusion will be the historical level for that patient after a washout or, if below the limit of detection of the local assay, zero (0) will be used.

Name of Sponsor/Company: Octapharma AG	
Name of Investigational Product: Octafibrin	Protocol Identification Code: FORMA-04
Name of Active Ingredient: Fibrinogen	Date of Final Protocol: 30-May-2017

#### **Dosing for On-Demand Treatment of Bleeding**

For each bleeding episode that is treated as part of the study, each subject will receive at least 1 infusion of *Octafibrin* for the treatment of a major or minor acute bleeding episode on Day 1.

*Octafibrin* will be individually dosed to achieve a recommended target fibrinogen plasma level dependent on the bleeding type (minor or major).

- **Minor bleeding** will be treated to achieve a recommended target fibrinogen plasma level of 100 mg/dL and an accepted lower limit of 80 mg/dL.
- **Major bleeding** will be treated to achieve a recommended target fibrinogen plasma level of 150 mg/dL and an accepted lower limit of 130 mg/dL.

On subsequent study days, fibrinogen plasma levels will be measured daily to determine whether additional infusions of *Octafibrin* are needed:

- **Minor bleeding** will be observed for at least 3 days.
- **Major bleeding** will be observed for at least 7 days.

#### **Additional Octafibrin infusions, as required**

- Additional infusions of *Octafibrin* **should** be administered if the actual fibrinogen plasma level measured on subsequent study days is below the accepted lower limit of the target level (80 mg/dL for minor bleeding, 130 mg/dL for major bleeding).
- If the actual fibrinogen plasma level is above the accepted lower limit of the target level, *Octafibrin* **should not** be administered.

#### **Definition of minor and major bleeding**

- **Minor bleeding** events are defined as mild haemarthrosis or superficial muscle, soft tissue, and oral bleeding.
- **Major bleeding** events are defined as symptomatic bleeding in a critical area or organ, such as intracranial, intraspinal, intraocular, retroperitoneal, intraarticular, or pericardial bleeding, or intramuscular bleeding with compartment syndrome, or bleeding causing a decrease in haemoglobin level by 20 g/L (1.24 mmol/L) or more.

Characterisation of any other bleeding events not within these categories will be discussed individually with the investigator.

#### **Dosing for Surgery**

For each surgery that is treated as part of the study, within 3 hours prior to surgery, each subject will receive a loading infusion of *Octafibrin*.

Name of Sponsor/Company: Octapharma AG	
Name of Investigational Product: Octafibrin	Protocol Identification Code: FORMA-04
Name of Active Ingredient: Fibrinogen	Date of Final Protocol: 30-May-2017

*Octafibrin* will be individually dosed to achieve a recommended target fibrinogen plasma level dependent on the surgery type (minor or major).

- Patients undergoing **minor surgery** will be treated to achieve a recommended target fibrinogen plasma level of 100 mg/dL and an accepted lower limit of 80 mg/dL.
- Patients undergoing **major surgery** will be treated to achieve a recommended target fibrinogen plasma level of 150 mg/dL and an accepted lower limit of 130 mg/dL.

On each post-operative day, fibrinogen plasma levels will be measured daily to determine whether maintenance infusions of *Octafibrin* are needed:

- **Minor surgery** will be observed for at least 3 post-operative days.
- **Major surgery** will be observed for at least 7 post-operative days.

#### **Maintenance infusions, as required:**

- Additional infusions of *Octafibrin* **should** be administered if the actual fibrinogen plasma level measured on subsequent study days is below the accepted lower limit of the target level (80 mg/dL for minor surgery, 130 mg/dL for major surgery).
- If the actual fibrinogen plasma level is above the accepted lower limit of the target level, *Octafibrin* **should not** be administered.

#### **Definition of minor and major surgery**

Surgeries are defined as **major**, if any of the following criteria are met:

- Requiring general or spinal anaesthesia.
- Requiring opening into the great body cavities.
- In the course of which hazards of severe haemorrhage is possible.
- Requiring haemostatic therapy for at least 6 days.
- Orthopaedic interventions involving joints (ankle, knee, hip, wrist, elbow, shoulder).
- Surgeries/conditions in which the subject's life is at stake.

Characterisation of any other surgery not within these categories and considered major by the investigator will be discussed individually with the investigator.

All other surgeries are classified as minor. The classification is made prospectively.

#### **Duration of Treatment:**

**Planned duration over the entire study:** The planned study duration is up to 5 years. The study will be considered completed when a minimum of 12 subjects have undergone PK assessments, 6 subjects (i.e., at least 3 subjects aged between 0 and <6 years and 3 subjects aged between 6 and <12 years) have at least one documented bleeding episode, and a minimum of 2 surgical procedures have been performed.

Name of Sponsor/Company: Octapharma AG	
Name of Investigational Product: Octafibrin	Protocol Identification Code: FORMA-04
Name of Active Ingredient: Fibrinogen	Date of Final Protocol: 30-May-2017

**Planned duration for an individual subject:**

All patients (at least 12) will undergo a PK study after screening. This will have a duration of 14 days, after which a patient can be treated for a bleeding episode or planned surgical procedure when they occur.

For subjects receiving on-demand treatment,

- The individual **subject observation and follow-up period** for each documented episode starts with the first dose of *Octafibrin* administered for on-demand treatment of an acute bleeding episode (Day 1) and will be followed up to at least Day 30.
- Each subject's **treatment observation period** is defined according to the severity of the event and will last at least 3 days for minor and 7 days for major bleeding episodes.

For subjects undergoing surgical prophylaxis,

- the **surgical observation period** starts with the first dose of *Octafibrin* administered prior to elective surgery (Day 1) and, depending on the severity of the event, will last at least 3 post-operative days for minor and 7 post-operative days for major surgeries or until the day of the last post-operative infusion, whichever comes last.

During the study observation period, enrolled patients will be treated for any bleeding episodes or planned surgeries that can be managed under the protocol. Patients may remain in the study until the 6th patient (at least 3 patients each in the specified age groups) has at least one documented bleeding episode and there are at least 2 surgical procedures documented.

As many bleeding episodes or surgeries as possible occurring throughout the study observation period will be documented. Only the first bleeding episodes will be used for the analysis of the primary endpoint. All bleeding episodes documented in the study will be assessed as a secondary endpoint.

Patients who were screened for the study but did not receive any IMP will be considered 'no treatment' patients and reported separately.

All patients completing the PK phase will also be analyzed separately, regardless of whether they received any IMP for the treatment of a bleeding episode or surgery.

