**Study Outcome Parameters (Primary and Secondary Endpoints):****Primary endpoint**

The primary endpoint is the **overall clinical assessment of the haemostatic efficacy of *Octafibrin*** in treating the first documented bleeding episode of each patient. The first bleeding episode covers the time period from the first *Octafibrin* infusion for the treatment of a bleeding episode until 24 hours (i.e., 1 day) after the last infusion or the end of the treatment observation period, whichever comes last.

The investigator's overall clinical assessment of haemostatic efficacy for bleeding will be based on a 4-point haemostatic efficacy scale (see table below). The final efficacy assessment of each patient will be adjudicated by the Independent Data Monitoring & Endpoint Adjudication Committee (IDMEAC). The number of subjects per outcome category will be assessed in the final analysis.

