### **Definitions of Pre-, Intra-, and Post-operative**

- **Pre-operative** refers to the time period covering the last 12 hours before the start of surgery.
- **Intra-operative** is defined as the time from the start of surgery to the end of surgery, i.e., the time of completion of the last suture.
- **Post-operative** refers to the time from the end of surgery to the Last Post-Operative Day.

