**6.1.4.3 Last Post-Operative Day**

The Last Post-Operative Day is either at least post-operative day 3 for minor and post-operative day 7 for major surgery or the day of the last post-operative infusion, whichever comes last.

The assessments performed on the Last Post-Operative Day are identical to those performed on any other post-operative day (see Section 6.1.4.2).

In addition, the following assessments will be performed on the Last Post-Operative Day:

- post-operative efficacy assessment by the haematologist (see Section 7.2.2.4)
- brief narrative describing the details of hospitalisation (start and end date, details of the procedure), follow-up, outcome, and efficacy of the intervention

The assessments performed on the Last Post-Operative Day conclude the surgical observation period. No further study-related assessments will be performed, unless safety concerns (e.g., ongoing AEs) require follow-up.

Patients may remain in the study until at least 12 patients have undergone PK assessments, the 6th patient (at least 3 patients each in the specified age groups) has at least one documented bleeding episode, and at least 2 surgical procedures have been documented. When the study is closed, all subjects having received any IMP will be asked to return for a Study Completion Visit as summarised in Section 6.1.5.

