## 10.5 Surgical Prophylaxis

Efficacy of *Octafibrin* in surgical prophylaxis will be assessed intra-operatively (at the end of surgery = after last suture) by the surgeon and post-operatively (at the last post-operative day) by the haematologist using two 4-point efficacy scales.

The primary analysis regarding haemostatic efficacy will be done on the adjudicated assessments by the algorithm described above and by the IDMEAC.

The following will be presented in frequency tables with descriptive statistics or in listings, depending on the number of surgeries:

- Number of subjects undergoing surgeries (minor, major, total)
- Number of surgeries, overall (minor, major, total)
- Surgery characteristics (type and site, pre-planned (yes/no), severity, expected and actual duration, expected and actual blood loss) will be listed.
- Details on treatment for surgical prophylaxis (number of exposure days and injections prior to surgery, dosing details, total amount of *Octafibrin*) will be listed.
- Pre-, intra-, and post-operative fibrinogen plasma levels, pre- and post-infusion will be listed.
- Efficacy evaluation by the surgeon at the end of the surgery and by the haematologist on the last post-operative day.
- Subjects who switch to another FIX product during a surgery will be considered treatment failures, i.e. the efficacy will be imputed to be “none” for each haemostatic efficacy assessment after the switch in the efficacy analyses for this surgery.
- Adjudicated overall efficacy assessment of the surgeries using the algorithm for the adjudicated intra- and post-operative assessments of haemostatic efficacy (as described in chapter 3.3.6 of this SAP). All assessments adjudicated by the IDMEAC will be listed together with the surgery details and the intra- and post-operative assessments of the surgeon and the haematologist.

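### When the last post-operative infusion falls on or after day 3 (minor) or day 7 (major), the surgical rating closes that same day, without the 24-hour tail used for bleeds

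*Protocol*

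**What the plan says.** **Surgery.** The synopsis (planned duration for an individual subject) sets a minimum of 3 post-operative days for minor and "7 post-operative days for major surgeries or until the day of the last post-operative infusion, whichever comes last". The same rule is in Protocol 3.1.2.2, 3.2.3, 6.1.4, 6.1.4.3 and 6.2.2, and in SAP 4.3.6 and 5.2. Protocol 6.1.4 adds that post-operative "refers to the time from the end of surgery to the Last Post-Operative Day". Protocol 6.1.4.3 places the haematologist's rating on that day, and SAP 10.5 agrees: "Efficacy evaluation by the surgeon at the end of the surgery and by the haematologist on the last post-operative day". Protocol 6.1.4.3 then states: "The assessments performed on the Last Post-Operative Day conclude the surgical observation period". It continues: "No further study-related assessments will be performed, unless safety concerns (e.g., ongoing AEs) require follow-up".

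**Bleeds.** The scored episode runs from the first infusion "until 24 hours (i.e., 1 day) after the last infusion or the end of the treatment observation period, whichever comes last" (synopsis; also Protocol 3.1.1, 7.2.1 and 9.3.1, SAP 4.3.1 and 10.1).

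**What else stops when the surgical period closes.**
- Non-serious adverse events are recorded to the Last Post-Operative Day (Protocol 3.2.3, 6.1.4).
- Concomitant medication, including other fibrinogen concentrates, is recorded for surgery only during the surgical observation period, apart from drugs used to treat serious events (Protocol 4.4.1).
- The SAP 10.5 rule that scores a product switch as a failure acts only on assessments made after the switch. It names a factor IX product; I read it as meaning another fibrinogen concentrate.

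**The concern.** The post-operative scale asks whether bleeding was controlled and, for its worst category, whether an alternate concentrate was used. If the final infusion is given on the closing day, the rating is due within hours of it. The last timed check is 1 hour after the infusion. A failure on the following day then falls outside the rated and recorded period, whereas the same failure in a bleed would fall inside it. The omission can only favour the product.

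Two other planned outputs need those same 24 hours. Membership of the SURG-PP set (SAP 6.1) requires no coagulation-active drug until 24 hours after the last infusion. The safety tables (Protocol 9.4, SAP 12) count adverse events within 24 hours of the end of an infusion. Neither can be fully evaluated when recording stops on the infusion day.

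**Working it through.** The study is descriptive and gives no sample size, power or error rate for this point, so there is no planned figure to reproduce. Four checks follow.

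**1. Which surgeries are affected.** Closing day = max(minimum day, day of last infusion). Days observed after the last infusion = closing day − day of last infusion.
- Minor (minimum 3): last infusion on day 0, 1 or 2 leaves 3, 2 or 1 days; on day 3 or later it leaves 0.
- Major (minimum 7): last infusion on day 0 to 6 leaves 7 down to 1 days; on day 7 or later it leaves 0.

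The gap exists only in the zero cases.

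**2. Whether a closing-day infusion is plausible.** Inputs: targets of 100 and 150 mg/dL and lower limits of 80 and 130 mg/dL (Protocol 5.4.4); half-life of 3–5 days under normal physiology (Protocol 1.1). Protocol 6.1.4.3 makes the closing-day assessments identical to those of other post-operative days, and the surgical flow chart gives that day its own pre- and post-infusion columns. Assume the level was at target, with no overshoot, 24 hours earlier, and that there is no endogenous fibrinogen.

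Level after 24 h = target × 2^(−1/half-life in days)
- Major: 150 × 2^(−1/3) = 119.1; 150 × 2^(−1/4) = 126.1; 150 × 2^(−1/5) = 130.6 mg/dL, against 130.
- Minor: 100 × 2^(−1/3) = 79.4; 100 × 2^(−1/4) = 84.1; 100 × 2^(−1/5) = 87.1 mg/dL, against 80.

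Half-life at which the level just reaches the limit after 24 h = ln 2 / ln(target/limit)
- Major: ln 2 / ln(150/130) = 4.84 days.
- Minor: ln 2 / ln(100/80) = 3.11 days.

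Sensitivity for major surgery with a constant endogenous 50 mg/dL, the entry ceiling: 50 + 100 × 2^(−1/3) = 129.4 to 50 + 100 × 2^(−1/5) = 137.1 mg/dL. Most of that range lies above the limit.

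**3. Effect of a missed failure under Table 4 (Protocol 7.2.2.4).** Suppose the post-operative rating should have dropped from excellent or good.
- To none: with an intra-operative rating of excellent, success becomes primary adjudication; with good, success becomes failure; with moderate, success (or primary adjudication, if the post-operative rating had been good) becomes failure.
- To moderate: with excellent, it stays success; with good, success becomes primary adjudication; with moderate, success or primary adjudication becomes failure.

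**4. Effect on the reported rate.** If one surgery does move from success to failure (exact Clopper-Pearson 95% intervals, for illustration; the SAP plans none for surgery):
- 2 surgeries, the minimum in most places: 2/2 = 100% (15.8–100) becomes 1/2 = 50% (1.3–98.7).
- 4 surgeries, the minimum in Protocol 3.1.2.2: 4/4 = 100% (39.8–100) becomes 3/4 = 75% (19.4–99.4).

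**The case against.** A reader might infer that the surgical period always ends with the last infusion and that a later failure cannot lower the result. The documents support neither.
- The 3- and 7-day minimum protects every surgery whose last infusion is earlier.
- The committee (IDMEAC) adjudicates with a review of the surgical case, and its assessment overrides the ratings (Protocol 7.2.2.4). A narrative of hospitalisation, follow-up and outcome is required.
- Serious events are reported throughout participation.
- A failure treated with more study product makes that infusion the last one and extends the period.
- The SAP lists a post-operative type of bleeding episode, so a later bleed treated with study product could be captured there.

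Nor is the haematologist rating blind. By day 3 or 7 there are daily wound, haematology and fibrinogen data, and a closing-day infusion may be prompted by a plasma level with no bleeding. The investigator's judgement sets treatment duration, so the last infusion can be identified without a next-day level. Finally, this is a secondary endpoint in a descriptive study, with no planned comparison of bleeds and surgeries, and nothing obliges the two windows to match.

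All of this stands, and it narrows the point. It does not close the gap, because case review can use only what has been collected. A non-serious re-bleed or a next-day switch to another concentrate has no scheduled route to the committee. Surgery has no Day 30 visit, and the next planned contact may be the Study Completion Visit. SAP 5.4 does say that concomitant medication is recorded throughout the trial, but Protocol 4.4.1 restricts it, and sites collect data under the protocol.

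**Conclusion.** The point holds in a conditional form. For surgeries whose last infusion falls on or after post-operative day 3 (minor) or 7 (major), rating and routine recording close on the infusion day. A non-serious failure in the next 24 hours can then count only if it reaches case review.

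The condition is realistic in major surgery, where the level 24 hours after target is about 119–131 mg/dL against 130. It is less likely in minor surgery (79–87 against 80). It would be tempting to call a closing-day infusion the expected case in major surgery. The figures do not go that far: the range straddles the limit, uses a normal-physiology half-life, and assumes no overshoot and no endogenous fibrinogen.

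With 2 surgeries, one missed failure could change the reported result from 1/2 to 2/2. That swing is not automatic; it depends on the intra-operative rating and on adjudication under Table 4. This is a modest weakness in a secondary endpoint, worth correcting because the correction is small and the protocol's bleed wording already supplies it.

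**What to change.** End the haematologist's rating, and the recording of adverse events, concomitant medication and product switches, at the later of post-operative day 3 (minor) or 7 (major) and 24 hours after the last post-operative infusion.

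Make the change everywhere the rule appears, so that no new contradiction arises:
- Synopsis: planned individual duration, surgical outcome parameters, assessments in surgical prophylaxis, and Last Post-Operative Day.
- The surgical flow chart.
- Protocol 3.1.2.2, 3.2.3, 6.1.4 (including the definition of post-operative), 6.1.4.3 and 6.2.2.
- SAP 4.3.6, 5.2 and 10.5, with the switch rule applied up to the new closing time.

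State that the added time is for rating and recording only and leaves the dosing rules as they stand. Without that sentence, the extra day could be read as another day of level-driven re-dosing, which would extend the window again. Reconcile SAP 5.4 with Protocol 4.4.1 on concomitant medication at the same time.

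Cost: amendment wording, and one further contact, up to one day later, in the affected surgeries only.
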